## 9.5 Study Size

In studies investigating the interferon-free ABBVIE REGIMEN ± RBV, SVR12 rates of about 95% were observed, even in difficult-to-treat CHC patients (e.g. cirrhotic G1a treatment experienced patients). To describe in routine clinical practice the effectiveness of the ABBVIE REGIMEN ± RBV in patients with CHC a precise estimate of the SVR12 rates in the core population of this study should be achieved (see Section 9.7.1 for the definition of the core population).

It is expected, that during the planned recruitment period of 12 months about 650 patients with ABBVIE REGIMEN ± RBV can be included into this observational study, and that at least 620 patients will be evaluable in the core population. As obvious from.

Table 3, if the SVR12 rate is at least 95%, then with 620 patients the width of the 95% confidence interval (CI) will not be wider than 3.5%. Even in the case that fewer patients will be enrolled and only 590 patients can be evaluated in the core population, the 95% CI will have a width of ≤3.6% for a SVR12 rate of 95%.

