### 9.7.3.3 Statistical Methods for Analysis of Effectiveness Variables

The simple percentage of patients achieving SVR12 will be calculated and a two-sided 95% confidence interval (CI) of the percentage based on the Wilson's Score method will be computed.

Corresponding methods will be used for other response rates (EoT response rate, relapse rate, viral breakthrough). The relapse rates will be estimated in patients of the CP analysis groups with EoT response and sufficient HCV RNA measurements post-treatment. Viral breakthrough rates will be estimated in all patients of the CP analysis groups, who have at least one undetectable HCV RNA measurement on-treatment and at least one on-treatment or EoT measurement thereafter.

Univariate and multiple logistic regression (MLR) methods will be used to investigate the impact of the following explanatory covariates on SVR12:

- Key demographic information
- Mode of CHC infection
- HCV RNA level at baseline
- Most recent stage of liver fibrosis
- HCV genotype and subtype (if available)
- Type of treating institute
- Liver and/or CHC related co-morbidities
- Key clinical chemistry and hematology laboratory variables at baseline
- In treatment experienced patients only:
  - Most recent prior treatment for CHC
  - Outcome of most recent prior CHC treatment

Further details and additional covariates will be specified in the SAP.

These analyses will be of exploratory nature, data driven, and will be repeatedly performed for the CP. Backward selection procedures will be applied to generate the final MLR models which consider only covariates for which the percentage of patients with available data is greater than 80% of the patient group analyzed. A p-value <0.05 will be used for the covariates to stay in the model in a backward elimination step. Logistic

---

Confidential Information

regression methods will also be used to investigate the impact of treatment adherence on SVR12.

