**Figure 1 - Study Flowchart**

### 3.2 Sample Size Calculation

In studies investigating the interferon-free ABBVIE REGIMEN  $\pm$  RBV, SVR12 rates of about 95% were observed, even in difficult-to-treat CHC patients (e.g. cirrhotic G1a treatment experienced patients). To describe in routine clinical practice the effectiveness of the ABBVIE REGIMEN  $\pm$  RBV in patients with CHC a precise estimate of the SVR12 rates in the core population of this study should be achieved (see Section 4.2.1 for the definition of the core population).

It is expected, that during the planned recruitment period of 12 months about 650 patients with ABBVIE REGIMEN  $\pm$  RBV can be included into this observational study, and that at least 620 patients will be evaluable in the core population. As obvious from Table 1, if the SVR12 rate is at least 95%, then with 620 patients the width of the 95% confidence interval (CI) will not be wider than 3.5%. Even in the case that fewer patients will be enrolled and only 590 patients can be evaluated in the core population, the 95% CI will have a width of  $\leq 3.6\%$  for a SVR12 rate of 95%.

**Table 1** Width of 95% Confidence Interval for SVR12

Number of patients	SVR12 rates	95% Confidence Interval*			Width
		Lower Limit	Upper Limit		
620	95%	93.0	96.5	3.5%	
590	95%	92.9	96.5	3.6%	
62	95%	86.5	98.3	11.8%	

\* exact two-sided 95% confidence interval according to Wilson's Score method

Assuming, that in total 620 patients will be evaluable, and subgroups of interest consist of at least 10% of the entire group (i.e.  $\geq 62$  patients), then the width of the 95% CI will be  $< 12\%$  for a SVR12 rate of 95%, which is also considered sufficiently precise for subgroup analyses.

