### **SVR12 (Exploratory Analyses)**

Univariate and multiple logistic regression (MLR) methods will be used to investigate the impact of various explanatory covariates (patient and disease characteristics) at baseline on SVR12.

These analyses will be of exploratory nature, data driven, and will be performed for CP population. Univariate logistic regression will be performed first and then backward selection procedures will be applied to generate the final MLR model. A p-value  $<0.05$  will be used for the covariates to stay in the model in a backward elimination step. If the percentage of patients with available data for a variable is lower than 80% of the patient group analyzed, then this variable will not be considered in the MLR analysis.

The variables to be considered are as follows:

- Key demographic information
  - Age (continuous)
  - Gender (Female [reference], Male)
  - Race/ethnic origin (White/Caucasian [reference], Black, Asian/Oriental, Other [all other races]); at least two categories with at least 10% of the patients each have to exists, so that this variable will be considered
  - Weight (continuous)
  - BMI (continuous)
  - IL28B, rs12979860 (CC [reference], CT or TT); patients with unknown genotype are excluded from the respective analyses.
- CHC disease characteristics
  - Years since diagnosis (continuous)
  - Mode of CHC infection (Drug use [reference], Other [all other answers excluding unknown], unknown);
  - Most recent stage of liver fibrosis (No cirrhosis/Transition to cirrhosis [reference], Cirrhosis; for definition see 4.2.6.2);
  - HCV RNA level at baseline ( $\log_{10}$  IU/mL)
  - HCV genotype (G1a\*, G1b, G4; for definition see section 4.2.6.2)
  - Type of treating institute (Private Practice / Private Hospital, Academic / University Hospital, General Hospital, Other)
  - Co-infections (every patient not reporting the respective co-infection is considered as not having the respective co-infection)
    - HIV (No [reference], Yes)
    - HBV (No [reference], Yes)
  - Liver and/or CHC related co-morbidities (every patient not reporting the respective co-morbidity is considered as not having the respective co-morbidity)
    - Liver transplantation (No [reference], Yes)
    - Steatosis (non-alcoholic) (No [reference], Yes)
    - Decompensated liver disease (No [reference], Yes)
  - Other co-morbidities (every patient not reporting the respective co-morbidity is considered as not having the respective co-morbidity)

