    - Depression (No [reference], Yes)
    - Diabetes mellitus (No [reference], Type 1/Type 2)

- Hypertension (No [reference], Yes)
- Immunologically mediated disease (No [reference], Yes)
- Hypothyroidism (No [reference], Yes)
- Alcohol use (None [reference], Yes –occasional, Yes –regular, Exdrinker)
- Key clinical chemistry and hematology laboratory variables at baseline
  - ALT ratio (continuous, see 4.2.6.5)
  - AST ratio (continuous, see 4.2.6.5)
  - Platelets [ $10^9/L$ ] (continuous)
- Prior treatment status (HCV treatment naïve [reference], HCV treatment experienced)

Additionally, an interaction term for cirrhosis status and genotype will be considered. If the most recent stage of liver fibrosis status (No cirrhosis/Transition to cirrhosis vs Cirrhosis), the genotype (G4, G1b vs G1a) or the interaction of both remains in the final model, then additional MLR might be considered for the subgroups concerned, taking into account the treatment regimen (e.g. in cirrhotic G1 patients: RBV vs no RBV and 12 wks vs 24 weeks).

The categories pre-specified above could be modified in the analyses if this is supported by the data (e.g. categories could be combined, if their impact on SVR12 is similar). Furthermore, continuous variables can be replaced by categorical variables.

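### The exploratory SVR12 predictor model starts backward elimination from up to 37 coefficients with about 31 expected failures, and has no shrinkage, internal validation or plan for separation

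*SAP*

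**What the plan says.** SAP 4.2.7.2.1, in the part on exploratory SVR12 analyses, runs univariate logistic regressions in the core population (CP) first; then "backward selection procedures will be applied to generate the final MLR model". No univariate screening threshold is given. Protocol 9.7.3.3 sets the retention rule: "A p-value <0.05 will be used for the covariates to stay in the model in a backward elimination step".

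The candidates follow the words "The variables to be considered are as follows" and cover demographics, disease characteristics, type of institution, co-infections, co-morbidities, alcohol, laboratory values and prior treatment status. The SAP continues: "Additionally, an interaction term for cirrhosis status and genotype will be considered".

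Two filters apply. "If the percentage of patients with available data for a variable is lower than 80% of the patient group analyzed", the variable is left out of the multiple model. Race is used only if at least two categories each hold at least 10% of patients. Categories may also be merged when their effect on SVR12 looks alike, and continuous variables may be turned into categories.

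Study size rests only on the precision of the SVR12 rate. Protocol 9.5 expects that "at least 620 patients will be evaluable in the core population", and SAP 3.2 takes as its basis that "SVR12 rates of about 95% were observed". Neither document gives a sample-size basis for the regression, a limit on events per coefficient, penalisation, internal validation, or a plan for separation.

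**The concern.** In a logistic model for SVR12 the information comes mainly from the rarer outcome, the failures. A regimen expected to succeed in 95% of patients leaves few of them, while the candidate list is long. Three consequences follow.

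- Testing many terms at 0.05 keeps some by chance.
- With sparse failures, some covariate levels contain none. The full model then has coefficients drifting to infinity, and the first elimination steps rest on unreliable tests.
- A term that survives does so partly because its estimate happened to be large, so reported odds ratios overstate the true effects.

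Predictive factors are the first-listed secondary objective in both documents, and the SAP introduction hopes that the findings may help optimise treatment. A reader who sees a final model with ordinary p-values and confidence intervals cannot tell how fragile it is.

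**Working it through.** **1. The plan's own figure.** Wilson interval without continuity correction: centre = (p + z²/2n)/(1 + z²/n), half-width = z·√(p(1−p)/n + z²/4n²)/(1 + z²/n), with p = 0.95 and z = 1.96. It gives 92.99–96.46 (width 3.47) at n = 620, 92.93–96.49 (3.55) at n = 590 and 86.49–98.26 (11.77) at n = 62. These match SAP Table 1 and the statement that "with 620 patients the width of the 95% confidence interval (CI) will not be wider than 3.5" percent. The planning inputs are therefore read correctly.

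**2. Coefficients (categories minus one).** Demographics 8 (race 3; age, gender, weight, BMI, IL28B 1 each); years since diagnosis 1; mode of infection 2; fibrosis 1; HCV RNA 1; genotype 2; institution 3; co-infections 2; liver co-morbidities 3; other co-morbidities 5; alcohol 3; laboratory 3; prior treatment 1. Sum: 35 from 27 variables. The interaction adds (2−1)×(3−1) = 2. Total: **37 coefficients in 28 terms**. Without race (3) and IL28B (1): 33 in 26 terms.

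**3. Failures per coefficient.**

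| N | Non-SVR12 | Failures | per 37 | per 33 |
|---|---|---|---|---|
| 620 | 5% (plan) | 31 | 0.84 | 0.94 |
| 590 | 5% (plan) | 29.5 | 0.80 | 0.89 |
| 620 | 10% (assumption) | 62 | 1.68 | 1.88 |
| 620 | 15% (assumption) | 93 | 2.51 | 2.82 |

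A variable can stay eligible with up to 20% missing, and covariates are not imputed. If 60–90% of patients are complete on all candidates (assumption), 31 failures become 31 × 0.6 = 18.6 to 31 × 0.9 = 27.9.

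**4. Chance retention with no true predictor.** Treating terms as independent: 28 × 0.05 = 1.4 expected, and 1 − 0.95²⁸ = 76% for at least one. With 26 terms: 1.3 and 74%.

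**5. Simulation of backward elimination.** N = 620, term-level p<0.05. Covariate prevalences and true odds ratios are assumptions, since the documents give none. An extreme start means at least one coefficient beyond 8 on the log-odds scale in the starting model.

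| True predictors | Test, coefficients, failures | Mean noise terms | ≥1 noise term | Noise share of selected | Extreme start | Runs |
|---|---|---|---|---|---|---|
| 0 | Wald, 37, 5% | 1.08 | 64% | 100% | 99% | 300 |
| 0 | Wald, 33, 5% | 0.92 | 61% | 100% | 96% | 120 |
| 0 | LR, 37, 5% | 1.73 | 77% | 100% | 93% | 30 |
| 1 (OR 2.5) | Wald, 37, 5% | 1.18 | 63% | 65% | 96% | 120 |
| 3 moderate | Wald, 37, 5% | 1.27 | 69% | 43% | 96% | 300 |
| 3 moderate | LR, 37, 5% | 1.67 | 77% | 52% | 97% | 30 |
| 3 strong | Wald, 37, 5% | 0.99 | 58% | 28% | 96% | 120 |
| 5 moderate | Wald, 37, 5% | 1.00 | 61% | 28% | 97% | 300 |
| 3 moderate | Wald, 37, 10% | 1.12 | 66% | 32% | 60% | 120 |

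LR = likelihood ratio. Three moderate: OR 2.5, 2, and 1.5 per SD. Three strong: OR 3, 3, and 2 per SD. Five moderate: the three moderate ones plus OR 2 and OR 1/1.5 per SD. The Monte Carlo standard error is about 3 points for 64% on 300 runs and about 8 points for 77% on 30 runs.

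**6. Optimism.** A separate run of 300 data sets with 37 pure-noise covariates and 5% failures gave an apparent AUC of 0.61 against a true 0.50. With one real predictor added (OR 1.5 per SD), it was kept in 61% of runs, with a geometric-mean OR of 1.74 when kept. On the log scale that is ln 1.74 / ln 1.5 = 0.554/0.405 = 1.37, an overstatement of about 37%.

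**The case against.** The strongest reply is that the SAP calls the analysis exploratory and data driven, and the stated aim is hedged. That stands, and it limits how much harm a weak model can do. It does not make an unstable fit stable, and it does not tell the reader how unstable the fit is.

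Second, 37 is a ceiling. The filters can bring it to 33, and the univariate step might screen further, although the SAP does not say so. This is fair, but 33 still leaves under one failure per coefficient at the planned rate, and screening on the same outcome does not remove selection bias.

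Third, 31 is the planning case. SAP 4.2.3 counts SVR12 still missing after imputation as failure, and Protocol 9.9 expects missing data to lower the observed rate. More events are plausible, hence the 1.7–2.5 range. The added events reflect missed follow-up, so the model would partly describe who returned for testing.

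Fourth, a reader might infer that the selected predictors will largely be noise. The documents do not support that. It follows only if there are no true predictors or about one. The Protocol's figures make zero signal doubtful: without ribavirin, Table 1 gives 90% in non-cirrhotic, treatment-naïve genotype 1a against 99% in 1b, and Section 7.1 reports 80% in cirrhotic 1a null responders treated for 12 weeks. The Protocol also says that many established predictors were not predictive in the development trials. The truth is therefore open.

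**Conclusion.** The model is over-parameterised for the planned number of failures, and the plan contains no safeguard. The firm parts are the counts: at most 37 coefficients (33 after filters) against 31 failures at N = 620 and 95% SVR12.

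With no true predictor, the chance of at least one noise term is roughly 60–77%, depending on the test used and the filters. The starting model had an extreme coefficient in 93–99% of simulated data sets at 5% failures, and in 60% at 10%. Retained odds ratios are biased away from 1. The simulated figures rest on assumed prevalences and effects and are approximate. The noise share among selected terms ran from 28% to 100% across the scenarios, so no single figure can be claimed.

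The primary SVR12 estimate is not affected. This is a cheap improvement to a secondary, exploratory analysis.

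**What to change.** - Keep the candidate list that Protocol 9.7.3.3 calls for, but fit the multiple model with Firth or ridge-penalised logistic regression. Firth fits more easily with the Protocol's backward step; ridge shrinks terms instead of removing them. Either keeps estimates finite, but neither corrects for selection, so the next items are also needed.
- Do not merge categories or choose cut-points according to their observed association with SVR12. Base any merging on category size alone.
- Bootstrap the whole procedure, including elimination. Report how often each term is selected, and an optimism-corrected AUC beside the apparent one.
- State with the final model that its p-values and confidence intervals are not adjusted for selection.
- Apply the same rules to the adherence models, which reuse this method, including in the smaller group taking ribavirin.
- Optionally, add a sensitivity model limited to baseline predictors named in Protocol 7.2: genotype/subtype (2 coefficients), viral load, fibrosis stage, age and prior treatment (1 each). That is 6 coefficients, or 31/6 ≈ 5.2 failures each. It would not be blind to outcome, because SVR12 covariate analyses were already run at the second to fourth interim analyses and are planned for the fifth. The report should say so.

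Replacing the main model with such a short list is not advised. It would depart from Protocol 9.7.3.3 and from the aim of finding predictors that interventional trials missed.

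Cost: a SAP wording change and modest programming on data already being collected. The downside is shrunken, less striking estimates.

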### 9.4.1 Data to be Documented

This observational study covers three documentation periods, see Figure 1. An overview on data to be collected throughout the study is summarized in **Table 2**.

---

Confidential Information

No use or disclose outside AbbVie is permitted without prior written authorization from AbbVie  
Version 3.0. (22. Apr 2015) – Germany V3.0 (17. November 2016)

Page 24 of 63

After the patient has signed the patient authorization form, the following data will be documented in the eCRF, if available from the patient charts based on assessments done in physicians' routine clinical practice.

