#### 4.2.3 Handling of missing data

No data will be imputed for any effectiveness or safety analyses except for the analyses of the HCV RNA endpoints and certain PRO endpoints. The discussion of missing data imputation for the PRO endpoints is included in section 4.2.7.2.3.

HCV RNA values will be selected for an RVR, EOTR and SVR analysis based on visit windows as defined in Table 4. When there is no HCV RNA value in a visit window based on defined visit windows, the closest values before and after the window, regardless of the value chosen for the subsequent and preceding window, will be used for the flanking imputation described below. For analysis of RVR, EOT and SVR, if a subject has a missing HCV RNA value at a post-Day 1 visit but with undetectable or unquantifiable (LLoD or LLoQ  $\leq$ 50 IU/mL) HCV RNA levels at both the preceding value and succeeding value, the HCV RNA level will be considered undetectable or unquantifiable, respectively, at this visit for this subject. In addition, if a subject has an

unquantifiable HCV RNA level at the preceding value and an undetectable HCV RNA level at the succeeding value, or vice versa, the HCV RNA level will be imputed as unquantifiable at this visit for this subject.

For analyses of RVR, subjects still missing a value for the visit after flanking imputation will be considered as a failure. For EoTR and SVR analysis, if there is no value in the appropriate window after flanking imputation but there is an HCV RNA value after the window, then it will be imputed into the EoTR or SVR window respectively. Subsequent to this flanking and backward imputation, if the HCV RNA value remains missing at a specific time point, then the subject will be considered as virological failure at this time point (i.e., not undetectable or unquantifiable).

If a subject starts another treatment for HCV, then all HCV RNA values for this subject measured on or after the start date of the new HCV treatment will be excluded from analyses. The subject will be considered a failure for summaries of viral response at all time points after the start of the new HCV treatment.

Due to the non-interventional nature of this study several different methods for determination of the HCV RNA value can be applied. For the purpose of the statistical analysis, a HCV RNA measurement is considered <50 IU/mL,

- if a PCR test was used

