### **Adherence**

Adherence will be displayed for the CP by genotype and cirrhosis status and for the SP by treatment regimen and cirrhosis status. Summary statistics (n, mean, median, standard deviation [SD], and range) will be generated for continuous variables. Numbers and percentages of patients will be presented for categorical variables.

- Adherence to ABBVIE regimen (% of target dose [adherence=cumulated number of pills taken /(initial prescribed number of pills x planned duration)])
  - >105%
  - >95%-<=105%
  - >80%-<=95%
  - >50%-<=80%
  - <=50%
- Adherence to ribavirin (% of target dose [adherence=cumulated dose taken /(initial prescribed dose x planned duration)])

- >105%
  - >95%-<=105%
  - >80%-<=95%
  - >50%-<=80%
  - <=50%
- Percentage of actual treatment duration in relation to the target duration of ABBVIE regimen taken
- Deviating duration of ABBVIE regimen
  - Early discontinuation (actual duration is shortened for more than 7 days)
  - Not deviated
  - Exceedance (actual duration is prolonged for more than 7 days)
- Method used to document adherence (Interview, Diary)
- Percentage of actual days with treatment with RBV in relation to the planned duration
- Ribavirin earlier discontinued than ABBVIE regimen
- Initial dose of Ribavirin
  - 1000 mg/day
  - 1200 mg/day
  - XXX
- Cumulative dose of Ribavirin (g)
- Dose modifications/termination of RBV [in patients taking RBV, for a patient more than one dose modification and its main reason could be reported, but for each single reason the patient is counted only once] (Total number of patients with lower dose than highest previous dose [including patients who stopped the treatment earlier], Anemia, Nausea/Vomiting, Rash, Other [including patients who discontinued ABBVIE regimen earlier, but did not stop the RBV treatment before the ABBVIE regimen])

In addition to the summary statistics of the adherence variables, logistic regression analyses will be performed for the following adherence variables: "adherence to ABBVIE regimen" in all patients of the CP, "adherence to ribavirin" in all patients of the CP taking RBV, each categorized as follows: >=95%, >80%-<=95%, <=80% to investigate the additional impact of overall treatment adherence on SVR12. The categories may be changed if they are sparsely filled. Adherence will be included as mandatory covariate in addition to the baseline explanatory variables already mentioned above. Also the same methods will be applied as described above.

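### The 80% availability rule works one covariate at a time, so the SVR12 predictor and adherence models can lose many patients and failures to joint missingness, and no refit on the retained covariates is planned

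*SAP*

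**What the plan says.** SAP 4.2.7.2.1, under SVR12 (Exploratory Analyses), plans univariate logistic regressions followed by backward elimination with p<0.05 to stay. A covariate is left out of the multiple regression under one condition on completeness: "If the percentage of patients with available data for a variable is lower than 80% of the patient group analyzed". Protocol 9.7.3.3 has nearly the same rule but admits only covariates with availability "greater than 80% of the patient group analyzed", so the two differ only at exactly 80%. Both rules look at a single variable.

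On missing values, SAP 4.2.3 states: "No data will be imputed for any effectiveness or safety analyses except for the analyses of the HCV RNA endpoints and certain PRO endpoints". Some covariates nevertheless have a default in 4.2.7.2.1. Unreported co-infections and co-morbidities count as absent, mode of infection has an unknown category, and unknown genotype 1 subtype is grouped with 1a. Patients with unknown fibrosis status are outside the core population (CP) under SAP 4.2.1. For IL28B, patients with unknown genotype are excluded from the analyses concerned.

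The adherence regressions add adherence as a mandatory covariate to the same baseline list, and the SAP says: "Also the same methods will be applied as described above". Protocol 9.4.1 explains why gaps are to be expected. Data are entered "if available from the patient charts based on assessments done in physicians' routine clinical practice".

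**The concern.** Several candidates have neither a default nor an unknown category: weight and BMI, years since diagnosis, baseline HCV RNA, the ALT and AST ratios (which also need the local upper limit of normal), and platelets. Alcohol use may belong here too. It depends on whether its bullet falls under the co-morbidity default, which is not clear. Adherence has no missing-value rule either.

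A logistic model cannot use a record with an empty covariate. Backward elimination normally compares models on the same records, so a patient who lacks one candidate is lost at every step, even if that candidate is eliminated at once. A set of variables that each pass the 80% test can therefore leave far fewer than 80% of patients. The SAP sets no minimum number of complete records or failures and does not refit the final model on the patients who have the covariates it keeps.

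Two secondary objectives rest on these models: predictive factors of response and the influence of adherence. With SVR12 expected near 95%, failures are the scarce quantity, and each failure lost widens the intervals around the odds ratios.

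**Working it through.** **Inputs.** SAP 3.2 expects that "at least 620 patients will be evaluable in the core population" and cites earlier studies in which "SVR12 rates of about 95% were observed". Expected failures: 620 × 0.05 = 31. In the SAP's reduced case, where "only 590 patients can be evaluated in the core population", the figure is 590 × 0.05 = 29.5. The documents give no missing rate for any covariate, so the rates and groupings below are assumptions.

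**The plan's own figure.** The documents state none for the regressions. Table 1 of the SAP gives 95% interval widths for SVR12 of 3.5, 3.6 and 11.8 points for 620, 590 and 62 patients. The Wilson score formula without continuity correction gives 3.47, 3.55 and 11.77, so the table reproduces. It concerns the simple SVR12 percentage and does not cover the regressions.

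**Grouping.** Candidates that tend to be missing together form one block.
- Six blocks: weight/BMI, years since diagnosis, baseline HCV RNA, alcohol use, ALT/AST ratio, platelets.
- Three blocks: weight/BMI, years since diagnosis, and all the blood tests together, with alcohol use covered by the co-morbidity default.

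IL28B, race and prior treatment status can also be incomplete. They are left out here. IL28B may fall below 80%, and race must first meet its own 10% rule.

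**Formulas.** With missing fraction m per block and k blocks, the share complete on all is (1 − m)^k if blocks are missing independently. It is 1 − m if missingness is fully nested, meaning the same patients lack everything. Each share is multiplied by 620 and by 31, which assumes failures and responders are deleted at the same rate.

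| Missing per block | Six blocks, independent | Three blocks, independent | Fully nested |
|---|---|---|---|
| 5% | 0.95^6 = 0.735: 456 patients, 22.8 failures | 0.95^3 = 0.857: 532 patients, 26.6 failures | 0.95: 589 patients, 29.4 failures |
| 10% | 0.90^6 = 0.531: 329 patients, 16.5 failures | 0.90^3 = 0.729: 452 patients, 22.6 failures | 0.90: 558 patients, 27.9 failures |
| 20% (limit) | 0.80^6 = 0.262: 163 patients, 8.1 failures | 0.80^3 = 0.512: 317 patients, 15.9 failures | 0.80: 496 patients, 24.8 failures |

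**Adherence models.** Missing adherence adds one block. At 10%, and independent of the rest, it multiplies the shares by 0.90: 0.729 × 0.90 = 0.656 and 0.531 × 0.90 = 0.478. The ribavirin model starts from fewer patients, a number the documents do not give.

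**With a refit.** If the final model kept one incomplete block at 10% missing, the refit would use 620 × 0.90 = 558 patients and 27.9 failures, against 329 to 452 patients and 16.5 to 22.6 failures under independence.

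**The case against.** The strongest reply is that the mechanism is inferred. Apart from IL28B, the SAP never says that incomplete records are deleted, and it does not say that elimination starts from the full list. If the univariate step is used to screen candidates, fewer blocks enter and the loss shrinks. This stands, and it is why the conclusion is worded as what would normally happen. The SAP specifies neither a screen nor a refit.

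A second reply is that the no-imputation sentence in 4.2.3 introduces a section about HCV RNA and PRO values, while 4.2.7.2.1 itself fills some covariates by default. A reader might infer an absolute ban on covariate imputation; the text is not that clear. It does name effectiveness analyses in general, though, and the regressions stand under the secondary effectiveness variables. No method is offered for the remaining covariates.

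Third, the size rests on chosen assumptions. The 26% figure needs six independent blocks, all at the limit. Baseline blood tests are likely to be missing together, and Protocol 9.6.1 and 9.8 provide data checks and queries. This also stands, so the range and the nested case are shown beside it.

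Fourth, a reader might infer that the odds ratios are biased because the complete records are selected on documentation. The documents do not show this. In a correctly specified logistic model, selection that depends only on covariates, or only on the outcome, leaves the slope odds ratios unbiased; bias needs joint dependence. SAP 4.2.3 counts missing SVR12 as failure, so a link between poor documentation and failure is plausible, but plausibility does not establish bias.

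Finally, the analyses are declared exploratory. That limits the weight of the point but does not remove the benefit of a nearly free refit.

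**Conclusion.** The concern holds as a loss of precision in the multiple regressions for predictors and adherence. Under three to six independently missing blocks, about 74–86% of patients and failures remain at 5% missing, 53–73% at 10% and 26–51% at the permitted 20%. Under full nesting, 95%, 90% or 80% remain. The plan tolerates this whole range without saying which case applies. The failure counts assume 620 patients, 95% SVR12 and equal deletion in failures and responders.

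It would go too far to say that the predictive-factor objective as a whole is answered in a documentation-selected subset. Each univariate model needs only its own covariate, and the SVR12 rates by genotype and cirrhosis status use all CP patients. The primary SVR12 estimate is not affected.

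**What to change.** In SAP 4.2.7.2.1, state how records with missing covariates are handled during selection. After backward elimination, refit the final predictor model and each adherence model on all CP patients with data for the retained covariates, including the mandatory adherence term. For ribavirin adherence, use all CP patients taking ribavirin who have those data. Report the number of patients and of SVR12 failures for both the selection model and the refitted model.

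The cost is a few sentences and one extra fit per model, with no new data. The table shells in SAP Part II are not among the documents here; if they already show these counts, only the refit is new.

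Multiple imputation of the baseline covariates may be added as an optional sensitivity analysis, with a sentence saying that the no-imputation rule in 4.2.3 does not bar it. It need not be the main analysis. It brings a missing-at-random assumption and selection on pooled tests, and it does not cure the shortage of failures: about 31, against about 37 parameters if every candidate and the interaction enter. The refit does not cure that either. It recovers patients for the final estimates, while selection itself still runs on the complete records.
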